7.1.8 Diagnostic impact

The number and frequency of the changes of radiological diagnosis, the increase in confidence of the diagnosis and the quality of the image, the confidence in diagnosis at the time of referral before and after CE/MRI(MRA), quality of the image stratified by age, country (CSP), site (CSP) and by GBCA (GBCAP), type of referral, quality of referral notes stratified by seniority, type of referral, seniority, specialty, repeat scans, reason for repeat scans and reason for repeat scans stratified by type of referral will be analysed for all patients (FIP), by site (CSP), by specialty (SPP) and by GBCA (GBCAP).

In addition, the change in radiological diagnosis and the change in increase of confidence will be shown in a bar chart for the different categories of quality of referral notes.

The quality of the image will be shown in a bar chart for the different categories of the change in radiological diagnosis and the confidence in diagnosis.

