3.2.1.3 Medical summary

- Diagnosis to which MR scan has been indicated
- Question to be answered with the use of CE-MR
- Secondary diagnosis
- Reason for using a contrast medium (border delineation of pathology, overall morphological characterization of pathology/lesion, overall increase in resolution of images required, confirmation of opinion/diagnosis, for comparison with non-contrast enhanced images, angiography or myocardial assessment, standard procedure for this diagnostic question, other)
- Specific reason why the GBCA was used
- Comorbidities (none, allergy, diabetes mellitus, heart failure, hepatic impairment, hypertension, neurologic symptom, renal impairment, autoimmune disease, malignancy/cancer, other)
 - Allergy status for patients with allergies (bronchial asthma, eczema, food allergy, urticaria, previous history of allergy to other contrast media [unknown media, Iodine-based media, Gadolinium-based media, ultrasound media, other media])
 - Renal status eGFR for patients with renal impairment (< 15, 15-30, 31-60, > 60 mL/min/m², impaired [exact eGFR unknown], unimpaired [exact eGFR n/a])
 - If renal status < 60 mL/min/m²: status of renal replacement for the compromised kidney(s) (renal replacement – dialysis, renal transplant, no replacement)
- Pre-medications (none, steroids, anti-histamines, other)
- Concomitant medications (no co-medication, chemotherapy/active treatment for malignancy, radiotherapy, anti-hypertensives, diabetic medications, heart failure treatment, nephrotoxic medication [antibiotics, iodinated agents, oncological drugs, immunosuppressants, other], other)
- Source of funding for the scan (self-funded [n/a, full, partially], paid by personal/hospital insurance, reimbursed by the state)

- If funding = insurance or reimbursed, what is being paid for (contrast media, procedure, procedure including contrast media)

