3.2.1.4 Referral details

- Quality of referral notes (not enough information, satisfactory levels of information, detailed information with clear medication)
- Referral type (routine, emergency, follow-up, repeat scan identical to previous scan)
 - If repeat scan, reason for repeat scan (poor quality image [patient-related factors, contrast-related factors, imaging-technique related factors], other)
- Referring physician seniority (resident, registrar or equivalent; consultant or equivalent; consultant with a specialist interest in the field)
- Referring physician specialty (cardiology, gastroenterology, gynecology, internal medicine, neurology, oncology, orthopedics, respiratory medicine, rheumatology, urology, other)

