3.2.1.6 Diagnosis after MRI

- Did contrast enhanced MRI change radiological diagnosis (yes, no)
- Did contrast enhanced MRI increase the radiologist's confidence in diagnosis compared to non-contrast enhanced MRI (yes, no)
- Radiologist's confidence in diagnosis at the time of referral, before CE-MRI (visual analogue scale 0-100%)
- Radiologist's confidence in diagnosis at the time of referral, after CE-MRI (visual analogue scale 0-100%)
- Quality of CE-MRI image (poor/inadequate, fair/partial, good/adequate, excellent)

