5.3 Covariates and subgroups

Endpoints will additionally be stratified by site, specialty, country, GBCA type, scanner type, scanner field strength, scan modality where applicable

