APPENDIX 1: LIST OF TABLES/FIGURES/LISTINGS

Table	1.1	Subject disposition and analysis populations
Table	1.2	Subject disposition and analysis populations by site
Table	1.3	Subject disposition and analysis populations by specialty
Table	2.1	Observation period
Table	2.2	Observation period by site
Table	3.1	Demographics and baseline characteristics
Table	3.2	Demographics and baseline characteristics by site
Table	3.3	Demographics and baseline characteristics by specialty
Table	3.4	Demographics and baseline characteristics by GBCA
Table	3.5	Main reason for using contrast media by GBCA
Table	4.1	Medical history
Table	4.2	Medical history by site
Table	4.3	Medical history by GBCA
Table	4.4	Number and frequency of previous scans by country
Table	5.1	Funding
Table	5.2	Funding by country
Table	5.3	Funding by specialty
Table	5.4	Funding by GCBA
Table	6.1.1	Referral
Table	6.1.2	Referral by site
Table	6.1.3	Referral by country
Table	6.1.4	Repeat scans by type of referral
Table	6.2.1	Repeat scans by type of referral by site
Table	6.2.2	Repeat scans by type of referral by country
Table	6.2.3	Repeat scans by type of referral by specialty
Table	6.2.4	Repeat scans by type of referral by GBCA
Table	7.1	Injection and scanning
Table	7.2	Injection and scanning by site
Table	7.3	Injection and scanning by country
Table	7.4	Injection and scanning by specialty
Table	7.5	Injection and scanning by GBCA
Table	7.6	Injection and scanning by scanner type
Table	7.7	Injection and scanning by scanner field strength
Table	7.8	Injection and scanning by scan modality
Figure	7.9	Bar chart of mean volume of contrast agent for type by sequence
Figure	7.10	Bar chart of mean volume of saline follow-up injection by type of sequence
Table	7.11	Sequence type by injection protocol
Table	7.12	Sequence type by injection protocol by site
Table	7.13	Sequence type by injection protocol by country
Table	7.14	Sequence type by injection protocol by age groups
Table	7.15	Sequence type by weight
Table	7.16	Injection dose
Table	7.17	Injection dose by GBCA
Table	7.18	Injection dose by indication
Table	7.19	Injection dose by age group
Table	7.20	Injection dose by GFR rate
Table	8.1	Diagnostic impact

Table	8.2	Diagnostic impact by site
Table	8.3	Diagnostic impact by specialty
Table	8.4	Diagnostic impact by GBCA
Table	8.5	Precision of the diagnostic criteria
Table	8.6	Precision of the diagnostic criteria by site
Table	8.7	Precision of the diagnostic criteria by specialty

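### Change of radiological diagnosis is compared between contrast agents, sites and specialties but never within scan purpose, so a difference between agents could reflect referral mix

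*SAP*

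**What the plan says.** The outcome is a single yes/no item in SAP section 3.2.1.6, "Did contrast enhanced MRI change radiological diagnosis (yes, no"), with a matching item for MRA in section 3.2.1.7. Section 7.1.8 opens with "The number and frequency of the changes of radiological diagnosis, the increase in confidence of the diagnosis and the quality of the image" and says that these, with other items, "will be analysed for all patients (FIP), by site (CSP), by specialty (SPP) and by GBCA (GBCAP"). The outputs are Tables 8.1 to 8.4, the last titled "Diagnostic impact by GBCA".

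Section 7 applies chi-square tests to categorical endpoints in stratified comparisons where feasible, and names GBCA as an example. Section 5.8 sets the significance threshold at 0.05. Effectiveness of the GBCAs is a secondary objective (section 2.1).

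The SAP captures the purpose of the scan in three ways:
- Reason for contrast (section 3.2.1.3), whose options include "confirmation of opinion/diagnosis, for comparison with non-contrast enhanced images".
- Referral type (section 3.2.1.4): "Referral type (routine, emergency, follow-up, repeat scan identical to previous scan").
- Category of the diagnostic question (section 7.1.3): rule-in, rule-out, refinement or clarification.

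None of these is a general stratifier. Section 5.3 reads: "Endpoints will additionally be stratified by site, specialty, country, GBCA type, scanner type, scanner field strength, scan modality where applicable". The one further breakdown of the change outcome in section 7.1.8 is that it "will be shown in a bar chart for the different categories of quality of referral notes" (Figure 8.13). Figure 8.20 charts image quality by change of diagnosis.

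**The concern.** A contrast scan in a patient without a diagnosis has more room to change the diagnosis than one done to confirm an opinion or to follow a known lesion. If that is so, the crude change rate of an agent depends on the mix of scans it was used for as well as on the agent.

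Agents are not allocated at random here. The SAP records the specific reason for using the GBCA (section 3.2.1.3) and whether the choice of medium is an individual or a collective decision at the centre (section 3.2.3). If the choice is largely made at centre level, agent and local case mix may be closely linked across the 14 planned sites.

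What is at stake is the reading of Table 8.4 and its p-value. A difference that only describes who was referred could be reported as statistically significant under a heading of diagnostic impact, in support of the effectiveness objective.

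**Working it through.** **Step 1: is the outcome crossed with scan purpose anywhere?** The SAP gives no expected change rate, effect size or power (section 4), so there is no figure to reproduce. The check is against section 7 and Appendix 1.

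| Scan-purpose variable | Where it is tabulated | Crossed with change of diagnosis? |
|---|---|---|
| Reason for contrast | 7.1.3; Table 3.5 by GBCA | No |
| Referral type | 7.1.6; Tables 6.1.1-6.1.3, and repeat scans in 6.1.4 and 6.2.1-6.2.4 | No |
| Diagnostic-question category | 7.1.3; Tables 8.9-8.12 (overall, site, specialty, GBCA) | No |

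Tables 8.12 and 8.4 would give the purpose mix and the change rate for each agent. These are two separate margins. The change rate within a purpose needs the joint table and cannot be recovered from them.

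**Step 2: how large could the effect be?** Every rate and share below is an assumption. Only the total of 5400 comes from the SAP (section 3.1, an upper limit). Take two agents with identical change rates within each purpose:
- p_o = change rate in other scans; p_f = change rate in follow-up or confirmation scans
- f = share of follow-up or confirmation scans for an agent
- Crude rate = f × p_f + (1 − f) × p_o
- Gap between agents A and B = (f_B − f_A) × (p_o − p_f)

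Example with p_o = 40%, p_f = 10%, f_A = 30%, f_B = 40%:
- A: 0.3 × 10% + 0.7 × 40% = 31%
- B: 0.4 × 10% + 0.6 × 40% = 28%
- Gap: 0.10 × 30 points = 3 points, although the difference within each purpose is zero.

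**Step 3: how often would the crude test give p<0.05?** With a two-sided 0.05 level and the opposite tail neglected, P = Φ((|p_A − p_B| − 1.96 × SE0) / SE1), where SE0 uses the pooled rate and SE1 the separate rates. For the example at 2700 per agent:
- SE0 = √(0.295 × 0.705 × 2/2700) = 0.0124
- SE1 = √((0.31 × 0.69 + 0.28 × 0.72)/2700) = 0.0124
- (0.030 − 0.0243)/0.0124 = 0.46, so P = 0.676

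| p_o / p_f | f_A / f_B | Crude A / B | Gap (points) | P, 2700 + 2700 | P, 1350 + 4050 | P, 500 + 500 |
|---|---|---|---|---|---|---|
| 40% / 10% | 30% / 40% | 31.0% / 28.0% | 3.0 | 0.676 | 0.558 | 0.179 |
| 40% / 10% | 30% / 50% | 31.0% / 25.0% | 6.0 | 0.998 | 0.989 | 0.561 |
| 40% / 20% | 30% / 40% | 34.0% / 32.0% | 2.0 | 0.346 | 0.275 | 0.099 |
| 40% / 20% | 30% / 50% | 34.0% / 30.0% | 4.0 | 0.883 | 0.782 | 0.273 |
| 30% / 15% | 30% / 40% | 25.5% / 24.0% | 1.5 | 0.247 | 0.201 | 0.079 |
| 30% / 15% | 30% / 50% | 25.5% / 22.5% | 3.0 | 0.733 | 0.615 | 0.198 |

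With equal shares the gap is zero and P is 0.05. A test stratified by purpose would also reject at about 5% in every row, because the within-purpose difference is zero throughout.

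**The case against.** Four points on the other side carry weight.

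- **The SAP gives no value to a change.** A reader might infer that no change is the intended, good result in confirmation and follow-up scans. The SAP nowhere says this, nor that a change is good. A follow-up scan may be done to look for something new. Section 3.2.1.6 does not define what the change is measured against, and the next item compares with non-contrast imaging. The point therefore rests only on the weaker inference that the likelihood and meaning of a change vary with purpose.
- **Purpose is not ignored.** Table 3.5 gives the main reason for contrast by GBCA, Tables 8.9-8.12 use the same four breakdowns as Tables 8.1-8.4, and the long sentence in section 7.1.8 lists type of referral among its items. That sentence could even be read as making referral type a stratifier, but no table in Appendix 1 bears that out. The case mix will be visible; only the cross-classification is missing.
- **Change is not the only measure.** Increase in confidence, confidence before and after contrast, and image quality are reported alongside it. They can show benefit when the diagnosis is unchanged, though none is planned within scan purpose.
- **The study is descriptive.** Section 1.2 states that no hypothesis is set in advance, and the tests are exploratory. Nothing in the SAP says that a lower rate will be taken as poorer effectiveness.

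These points limit the weight of the concern. They do not remove the gap, because a visible case mix beside a crude tested comparison still leaves the reader unable to separate the two.

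**Conclusion.** The point holds as a weakness of an exploratory secondary analysis. Change of diagnosis is compared crudely by GBCA, site and specialty, with a significance threshold and without stratification by scan purpose, although the variables needed are already in the plan.

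The size is unknown. In the assumed scenarios the spurious gap runs from 1.5 to 6 points, and the chance of p<0.05 from about 0.08 to nearly 1, depending on group size and imbalance. A more extreme assumption, follow-up shares of 70% against 30% with change rates of 10% and 40%, would give 19% against 31%. Nothing in the SAP shows that the agents differ in purpose mix at all.

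A reader might go further and conclude that differences between agents will be artefacts, or that follow-up and confirmation scans should be left out of the GBCA comparison. The document supports neither. In particular, repeat scans do not belong in one group with follow-up: section 3.2.1.4 names poor image quality as a reason for repeating a scan, and a changed diagnosis may then be the benefit sought.

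**What to change.** 1. In section 7.1.8 and Appendix 1, add tables of change of diagnosis by referral type, with follow-up and repeat scan kept separate, and by the diagnostic-question categories of section 7.1.3.
2. Make the exploratory GBCA comparison stratified by, or adjusted for, scan purpose, for example with a Cochran-Mantel-Haenszel test or logistic regression, instead of crude only. Keep all patients. Since section 5.5 does not replace missing values, give patients without a recorded purpose their own category.
3. Add a note to Tables 8.1-8.4 that a lower crude change rate is not by itself evidence of lower effectiveness.

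The cost is SAP wording and a few more tables from variables already collected or derived. The tables become longer and cells will be sparse for rarely used agents, so the limit to feasible tests in section 7 should apply here too. Adjustment for purpose does not remove other differences between agents, such as organ examined or prior imaging.

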5.8 Statistical significance (p-values)

A p-value of <0.05 will be declared as statistically significant.

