7 STATISTICAL METHODS

All continuous variables will be summarized using the following descriptive statistics: n (non-missing sample size), mean, standard deviation, median, minimum and maximum. The frequency and percentages (based on the non-missing sample size) will be reported for categorical measures. Data that will be listed will be sorted by country, site and subject.

For the comparison of endpoints in stratified analyses (e.g. by country, by GBCA etc.) explorative statistical tests will be applied (ANOVA for continuous endpoints, Chi-Square tests for categorical endpoints) if feasible.

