Table	8.8	Precision of the diagnostic criteria by GBCA
Table	8.9	Categories of diagnostic question
Table	8.10	Categories of diagnostic question by site
Table	8.11	Categories of diagnostic question by specialty
Table	8.12	Categories of diagnostic question by GBCA
Figure	8.13	Bar chart of mean change in radiological diagnosis by quality of referral notes
Figure	8.14	Bar chart of mean change in increase of confidence by quality of referral notes
Table	8.15	Quality of CE-MRI and CE-MRA
Table	8.16	Quality of CE-MRI and CE-MRA by age
Table	8.17	Quality of CE-MRI and CE-MRA by country
Table	8.18	Quality of CE-MRI and CE-MRA by site
Table	8.19	Quality of CE-MRI and CE-MRA by GBCA
Figure	8.20	Bar chart of mean quality of image by change in radiological diagnosis
Figure	8.21	Bar chart of mean quality of image by change in confidence for the diagnosis
Table	9.1	Staffing equipment
Table	9.2	Staffing equipment by country
Table	10.1	User satisfaction
Table	10.2	User satisfaction by country
Table	10.3	User satisfaction by GBCA
Table	11.1.1	Number of patients with adverse events by SOC and PT
Table	11.1.2	Number of patients with serious adverse events by SOC and PT
Table	11.1.3	Number of patients with adverse events by causality, SOC and PT
Table	11.1.4	Number of patients with adverse events by treatment, SOC and PT
Table	11.1.5	Number of patients with adverse events by severity, SOC and PT
Table	11.1.6	Number of patients with adverse events by time to onset, SOC and PT
Table	11.2.1	Number of patients with adverse events by site, SOC and PT
Table	11.2.2	Number of patients with serious adverse events by site, SOC and PT
Table	11.2.3	Number of patients with adverse events by site, causality, SOC and PT
Table	11.2.4	Number of patients with adverse events by site, treatment, SOC and PT
Table	11.2.5	Number of patients with adverse events by site, severity, SOC and PT
Table	11.2.6	Number of patients with adverse events by site, time to onset, SOC and PT
Table	11.3.1	Number of patients with adverse events by site, SOC and PT
Table	11.3.2	Number of patients with serious adverse events by country, SOC and PT
Table	11.3.3	Number of patients with adverse events by country, causality, SOC and PT
Table	11.3.4	Number of patients with adverse events by country, treatment, SOC and PT
Table	11.3.5	Number of patients with adverse events by country, severity, SOC and PT
Table	11.3.6	Number of patients with adverse events by country, time to onset, SOC and PT

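### Planned between-GBCA tests of image quality and diagnostic impact hold neither field strength nor indication constant, so a crude brand difference could reflect scan mix

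*SAP*

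**What the plan says.** Section 7.1.8 analyses change in radiological diagnosis, confidence and image quality, and states that they "will be analysed for all patients (FIP), by site (CSP), by specialty (SPP) and by GBCA (GBCAP"). For image quality it adds "quality of the image stratified by age, country (CSP), site (CSP) and by GBCA (GBCAP"). Appendix 1 carries this into Table 8.4 (diagnostic impact by GBCA) and Table 8.19 ("Quality of CE-MRI and CE-MRA by GBCA").

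Section 7 sets the method of comparison: "For the comparison of endpoints in stratified analyses (e.g. by country, by GBCA etc.) ", followed by "explorative statistical tests will be applied (ANOVA for continuous endpoints, Chi-Square tests for categorical endpoints) if feasible". Section 5.8 adds: "A p-value of <0.05 will be declared as statistically significant".

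The passage closest to an adjustment is in section 5.3: "Endpoints will additionally be stratified by site, specialty, country, GBCA type, scanner type, scanner field strength, scan modality where applicable". Section 3.2.1.5 records field strength in three levels (1.5T, 3T, >3T) and indication in three levels (CNS, organ/whole body, angiography). Section 7.1.7 derives dose in mmol/kg.

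**The concern.** Section 3.1 describes an observational study, so patients receive whichever agent the site or radiologist chose. A one-factor chi-square test or ANOVA across brands compares whole groups of patients as they happened to be scanned. If one brand is used more often at 3T, or more often for CNS examinations, and image quality or diagnostic yield differs by those conditions, the test picks up that difference and reports it under the brand's name. Sampling more patients does not cure this; it makes a spurious difference more likely to cross the threshold.

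At stake are Tables 8.4 and 8.19 and their p-values. They bear on the secondary objective in section 2.1, which concerns the effectiveness and safety profile of GBCAs, with the sponsor's agent named. A result below 0.05 in either table would be labelled statistically significant with nothing to show whether it survives a like-for-like comparison.

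**Working it through.** **Step 1. Which factors enter the by-GBCA comparison?**

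| Factor | Recorded or derived | In section 5.3 | In 7.1.8 or Tables 8.1–8.4, 8.15–8.19 | Crossed with GBCA for these endpoints |
|---|---|---|---|---|
| Field strength | 3.2.1.5 | yes, one-way | no | no |
| Indication | 3.2.1.5 | no | no | no |
| Dose (mmol/kg) | 7.1.7 | no | no | no |
| MRI or MRA | 3.2.1.5 to 3.2.1.7 | see objection | separate outcome variables | by variable definition |

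For injection and scanning, section 7.1.7 and Tables 7.6–7.8 do apply scanner type, field strength and scan modality. For the section 7.1.8 endpoints no matching table is listed. A table by field strength beside a table by brand would in any case not compare brands at the same field strength. The SAP contains no regression, matching, standardisation or stratified test.

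**Step 2. How large could the artefact be?** The SAP has no figure to reproduce: section 4 says the sample size has no statistical basis, and no rates are given. The following is an illustration on assumed inputs.

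- From the SAP: up to 5400 patients (section 3.1); threshold 0.05 (section 5.8).
- Assumed: two brands of 2700 each; no true brand effect; an excellent image in 40% of scans at 1.5T; a rate higher by g at 3T; 3T shares s_A and s_B for the two brands.

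Formulas: p_A = 0.40 + g·s_A and p_B = 0.40 + g·s_B, so the crude difference is d = g·(s_A − s_B). SE = √[p_A(1−p_A)/2700 + p_B(1−p_B)/2700]. Rejection probability = 1 − Φ(1.96 − d/SE) + Φ(−1.96 − d/SE).

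Worked case (b): p_A = 0.40 + 0.10×0.60 = 0.46; p_B = 0.40 + 0.10×0.40 = 0.44; d = 0.02; SE = √[(0.2484 + 0.2464)/2700] = 0.0135; d/SE = 1.48; rejection 0.315.

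| Case | g | 3T shares | p_A, p_B | d | Crude, formula | Crude, simulated | Stratified by field strength, simulated |
|---|---|---|---|---|---|---|---|
| (a) | 0.05 | 55% / 45% | 0.4275, 0.4225 | 0.005 | 6.6% | 6.3% | 5.3% |
| (b) | 0.10 | 60% / 40% | 0.46, 0.44 | 0.02 | 31.5% | 30.3% | 5.3% |
| (c) | 0.10 | 70% / 30% | 0.47, 0.43 | 0.04 | 84.1% | 83.9% | 4.7% |
| (d) | 0.20 | 70% / 30% | 0.54, 0.46 | 0.08 | about 100% | 100% | 4.8% |

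The simulated columns use 4000 runs, with a Mantel-Haenszel test as the stratified comparison. With 500 patients per brand instead of 2700, the formula gives 5.3%, 9.7%, 24.6% and 71.8% for (a) to (d). The artefact d is unchanged; only the chance of calling it significant falls.

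**The case against.** The strongest reply is that section 1.2 declares a descriptive study without a prior hypothesis, and that section 7 calls the tests explorative and applies them only where feasible. One-way tables suit a pattern-of-use study. This stands as a limit on severity. It does not remove the point, because sections 7 and 5.8 still attach p-values and a significance label to brand contrasts.

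Several stronger readings are tempting, and the SAP does not support them:

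- **That the secondary objective is a comparison of brands.** Section 2.1 says only that the study will look at effectiveness and safety. The comparison enters through section 7.
- **That field strength is ignored.** Section 5.3 is a general rule and section 7.1.8 need not repeat it. The narrower criticism is that Appendix 1 lists no such table for these endpoints and that a one-way breakdown does not adjust the brand contrast.
- **That no imaging condition is held constant.** Sections 3.2.1.6 and 3.2.1.7 record outcomes separately for MRI and MRA, with different quality categories. Section 3.2.1.5 assigns any MRA to the angiography indication, so that level is separated too. What remains is field strength, and CNS against organ/whole body within MRI.
- **That field strength, indication and dose are known to drive the endpoints, or that brands are known to be unevenly spread over scanners.** The SAP states neither. Section 1.1 treats a link between dose and field strength as an open question, and section 3.2.3 collects who decides on the agent.

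The illustration covers one binary image-quality endpoint. Confidence is rated before and after contrast, and its increase is judged against non-contrast imaging, so patient-level differences may partly cancel. No bias of a given size is shown for those endpoints.

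The term scan modality has two meanings (dynamic or delayed in section 3.2.1.5, MRA or MRI in section 7.1.7). That is a separate wording matter and adds nothing to this point.

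**Conclusion.** The point holds in this form: the SAP plans unadjusted between-GBCA tests at p<0.05 for image quality, change in diagnosis and confidence in a non-randomised study, while field strength and indication are available and unused in that contrast. Whether a crude difference would be an artefact depends on two things that the SAP does not give: how unevenly brands are spread over scanners and indications, and how strongly these influence the endpoints. Both are plausible and neither is established. Across the assumed cases with 2700 per brand, the false-positive rate of the crude test runs from about 6%, barely above nominal, to nearly 100%, while the stratified test stays at about 5%. That last result assumes that field strength is the only confounder and that patients are independent. Severity is minor to moderate, given the descriptive purpose.

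**What to change.** In section 7.1.8:

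1. State that by-GBCA results are reported separately for MRI and MRA.
2. Base any between-GBCA test on a comparison stratified by or adjusted for field strength (1.5T, 3T, >3T, pooling sparse levels) and, for MRI, indication (CNS against organ/whole body). A Cochran-Mantel-Haenszel analysis, or a regression that accounts for site, would serve.
3. Keep dose for a separate secondary model. It partly follows from the brand chosen, so adjusting for it changes the question.
4. Present the crude by-GBCA tables (8.4 and 8.19) without p-values and state that they are not comparative. Add the stratified tables or models to Appendix 1.

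The cost is SAP wording and a few extra tables or models on fields already collected. Rare brands will have thin strata, which must be pooled or only listed. If the sponsor does not want the extra analyses, dropping the between-GBCA tests and keeping the statement in item 4 would meet the main concern.
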